4.6 Demographics and Baseline Characteristics

The following summary and listing of demographic and baseline characteristics will be based on the FAS:

- A summary of demographic variables: age (years), sex, ethnicity, race, childbearing potential (female only), height (cm), weight (kg), BMI (kg/m^2) and LA grade by study treatment group and overall
- A summary of demographic variables by LA grade by study treatment group and overall
- A summary of viral serology results at baseline
- A summary of H.Pylori results at baseline
- Listing of demographics
- Listing of viral serology and H.Pylori at baseline

Age will be calculated as the number of complete years between a patient's birth date and the date of informed consent.

BMI is calculated automatically in eCRF as [weight/height²] (kg/m^2).

4.7 Medical/Surgical History

Medical/surgical history will be coded by primary system organ class (SOC) and preferred term (PT) using the latest version of the Medical Dictionary for Regulatory Activities (MedDRA) version 23.0 or higher.

In case of partial or completely missing start date and end date, if this is not possible to decide whether the medical condition is past or current, then it will be considered current.

Smoking history, alcohol consumption history and history intake of drugs and/or anabolic steroids will be presented together with duration of smoking (if former smoker), average number of units of alcohol consumed per week (if current consumption) and time since last drug intake (if former user).

The following summaries will be based on the FAS and provided by study treatment group and overall:

- previous medical conditions or events by MedDRA SOC and PT
- continuing medical conditions by MedDRA SOC and PT
- Smoking history, alcohol consumption history and history intake of drugs and/or anabolic steroids

The following listing will be provided:

- previous or continuing medical conditions or events
- Smoking history, alcohol consumption history and history intake of drugs and/or anabolic steroids

4.8 Prior and concomitant Medications and prior PPI Treatment

Prior and concomitant medications and prior PPI treatment will be coded using the latest available version of the World Health Organization Drug Dictionary (WHO-DD B3) Version March 2020 and will be classified by Anatomical Therapeutic Chemical (ATC) categories.

Medication start and stop dates will be compared to the date of treatment initiation to allow medications to be classified as either Prior only, both Prior and Concomitant, or Concomitant only. Medications starting after the completion/withdrawal date will be listed but will not be classified or summarized.

Medications that start and stop prior to the date of treatment initiation will be classified as Prior only. If a medication starts before the date of treatment initiation and stops on or after the date of treatment initiation, then the medication will be classified as both Prior and Concomitant. Medications will be classified as Concomitant only if they have a start date on or after the date of treatment initiation.

If medication start and/or stop dates are missing or partial, the dates will be compared as far as possible with the date of treatment initiation. If there is clear evidence to suggest that the medication stopped prior to the first dose of study medication, the medication will be assumed to be Prior only. Medications will be assumed to be Concomitant only, unless there is clear evidence (through comparison of partial dates) to suggest that the medication started prior to the date of treatment initiation. In that case, the medication will be assumed to be both Prior and Concomitant.

Where possible, if complete start and end date are available, duration (days) of medications will be calculated and included in listings as duration= end date – start date + 1.

The following summaries will be based on the FAS and provided by study treatment group and overall:

- Prior only medications
- Prior and concomitant medications
- Concomitant only medications
- Prior PPI treatment
- Prior PPI treatment by LA grade
- Newly prior PPI treatment (still on PPI treatment until 28 days prior to treatment initiation)
- Newly prior PPI treatment by LA grade (still on PPI treatment until 28 days prior to treatment initiation)

The following listing will be provided:

- Prior only medications

- Prior and concomitant medications
- Concomitant only medications
- Prior PPI treatment
- Newly prior PPI treatment (still on PPI treatment until 28 days prior to treatment initiation)

4.9 Treatment Exposure / Compliance

4.9.1 Treatment Exposure

Duration of exposure will be expressed in days and calculated for double blind phase, open label phase and overall:

Duration DB (days) = Date of last intake of study treatment in DB phase – date of first intake of study treatment in DB phase + 1

Duration OL (days) = Date of last intake of Lansoprazole in OL phase – date of first intake of Lansoprazole in OL phase + 1

Duration overall (days) = Date of last intake of study treatment – date of first intake of study treatment + 1

The total dose of X842 study drug will be calculated for the DB phase in each treatment group receiving X842, based on the number of tablets of X842 (or dummy) dispensed and returned.

Note that, in the DB phase, patients are supposed to take 4 tablets of X842 (or dummy) per day.

Total dose X842 DB (mg) = (Sum of number of tablets dispensed at start of DB phase - Sum of number of tablets returned at end of DB phase) x Daily dose /Nb of tablets per day

where daily dose is 50 mg, 100 mg, 150 mg or 200 mg depending on the treatment group and Nb of tablets per day is 4 for all treatment groups.

The total dose of Lansoprazole will be calculated for the DB phase (Lansoprazole group only), the open label phase (all treatment groups) and overall (Lansoprazole group only), based on the number of capsules of Lansoprazole (or dummy) dispensed and returned. Note that patients are supposed to take 1 capsule of Lansoprazole (or dummy) per day.

Total dose Lansoprazole DB (mg) = (Sum of number of capsules dispensed at start of DB phase - Sum of number of capsules returned at end of DB phase) x 30.

Total dose Lansoprazole OL (mg) = (Sum of number of capsules dispensed at start of OL phase - Sum of number of capsules returned at end of OL phase) x 30.

Total dose Lansoprazole Overall (mg) = Total dose Lansoprazole DB + Total dose Lansoprazole OL.

The following extent of exposure summaries will be presented on the Safety analysis set by treatment group:

- A Summary of the duration of exposure to treatment, by phase.
- A summary of the total dose of Lansoprazole and X842 by phase.
- Listing of exposure data.

4.9.2 Compliance

Compliance of each treatment group (the 4 X842 treatment groups and the Lansoprazole group) regarding the X842 study drug will be calculated for the DB phase based on the number of tablets of X842 (or dummy) dispensed and returned and on the duration of exposure in days in the DB phase.

Treatment compliance X842 DB (%) = (Sum of number of tablets dispensed at start of DB phase - Sum of number of tablets returned at end of DB phase) / (4 x Duration DB) x 100

Compliance of each treatment group (the four X842 treatment groups and the Lansoprazole group) regarding Lansoprazole study drug will be calculated for each phase based on the number of capsules of Lansoprazole (or dummy) dispensed and returned and on the duration of exposure in days in each phase.

Treatment compliance Lansoprazole DB (%) = (Sum of number of capsules dispensed at start of DB phase - Sum of number of capsules returned at end of DB phase) / (1 x Duration DB) x 100

Treatment compliance Lansoprazole OL (%) = (Sum of number of capsules dispensed at start of OL phase - Sum of number of capsules returned at end of OL phase) / (1 x Duration OL) x 100

Treatment compliance Lansoprazole Overall (%) = (Sum of number of capsules dispensed - Sum of number of capsules returned) / (1 x Duration Overall) x 100

The following compliance summaries will be presented on the FAS by treatment group:

- A summary of the treatment compliance measures by study phase
- A listing of treatment compliance

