1.3 Schedule of Assessments (SoA)

Details on procedures and timing of assessments are presented in Table 1.

Table 1 Overall Schedule of Assessments

Visit	Visit 1 Screening	Visit 2	Visit 3	Visit 4	Visit 5	Tel Visit 6	Tel Visit 7	Tel Visit 8	Visit 9 End of Study / Early Termination
Assessment/Study day	Day -7 ¹⁴ to Day 0	Day 0	Day 7 ±2 days	Day 14 ±3 days	Day 28 -2/+5 days	Day 35 ±3 days	Day 42 ±3 days	Day 49 ±3 days	Day 56 ±3 days
Assessment/Study week		Randomization	Week 1	Week 2	Week 4	Week 5	Week 6	Week 7	Week 8
Screening Period									
Informed consent	X								
Demographics	X								
Inclusion/exclusion criteria	X	X							
Medical/surgical history ¹	X								
Weight, height ²	X				X				X
Complete physical examination	X				X				X
Drugs of abuse	X								X
Viral serology testing ³	X								
Vital signs ⁴	X		X		X				X
12-lead ECG evaluation	X		X		X				X
Safety laboratory ⁵	X		X		X				X
H. pylori testing ⁶	X								

Visit	Visit 1 Screening	Visit 2	Visit 3	Visit 4	Visit 5	Tel Visit 6	Tel Visit 7	Tel Visit 8	Visit 9 End of Study / Early Termination
Assessment/Study day	Day -7 ¹⁴ to Day 0	Day 0	Day 7 ±2 days	Day 14 ±3 days	Day 28 -2/+5 days	Day 35 ±3 days	Day 42 ±3 days	Day 49 ±3 days	Day 56 ±3 days
Assessment/Study week		Randomization	Week 1	Week 2	Week 4	Week 5	Week 6	Week 7	Week 8
	Screening Period	Blinded Treatment Phase						Open-Label Phase	
Pregnancy test ⁷	X				X				X
Randomization		X							
Patients provided with study drugs for blinded phase		X	X	X					
Patients provided with Lansoprazole 30 mg for open-label phase					X				
PK blood sampling ⁸			X	X	X				
Upper endoscopy	X ¹⁵				X				
Symptom evaluation using QOLRAD Heartburn ⁹		X	X	X	X				X
Daily symptom diary (RESQ-eDiary) completion by patient		X	X	X	X	X	X	X	X
Symptom diary provision/training/review ¹⁰		X	X	X	X	X	X	X	X

Visit	Visit 1 Screening	Visit 2	Visit 3	Visit 4	Visit 5	Tel Visit 6	Tel Visit 7	Tel Visit 8	Visit 9 End of Study / Early Termination
Assessment/Study day	Day -7¹⁴ to Day 0	Day 0	Day 7 ±2 days	Day 14 ±3 days	Day 28 -2/+5 days	Day 35 ±3 days	Day 42 ±3 days	Day 49 ±3 days	Day 56 ±3 days
Assessment/Study week		Randomization	Week 1	Week 2	Week 4	Week 5	Week 6	Week 7	Week 8
Screening Period									
Symptom assessment by Investigator ¹¹	X	X	X	X	X	X	X	X	X
AE reporting ¹²	X	X	X	X	X	X	X	X	X
Prior/concomitant medications ¹³	X	X	X	X	X	X	X	X	X

Abbreviations: AE, adverse event; ECG, electrocardiogram; ICF, informed consent form; LA, Los Angeles; PK, pharmacokinetic.

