6.2 Preparation/Handling/Storage/Accountability

The blister packs containing the study medication will be dispensed as per randomization schedule by a site pharmacist or a registered nurse under supervision of other site personnel.

The Investigator will maintain a Drug Dispensing Log detailing the dates and quantities of study medication received, dispensed to and used by each patient and study medication returned or destroyed at the end of the study. Any discrepancies between dispensed and returned study drug must be explained and documented. Products deliberately and/or accidentally destroyed by the Investigator/pharmacy or the patient, must be accounted for. Patients will receive one additional blister pack at Visit 2/Day 0 to keep overage in case they return within the allowed visit window. Patients should return this additional blister pack for accountability at every visit and returned on Visit 5.

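### Double-blind dose and compliance formulas count drug dispensed at the start of the phase only, although drug is dispensed at three visits; read literally, an adherent patient can score well under 100%

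*SAP*

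**What the plan says.** SAP 4.9.2 defines tablet compliance in the double-blind phase as "Sum of number of tablets dispensed at start of DB phase - Sum of number of tablets returned at end of DB phase", divided by four times the duration of exposure and multiplied by 100. SAP 4.9.1 uses the same numerator for total X842 dose: the formula ends "Sum of number of tablets returned at end of DB phase) x Daily dose /Nb of tablets per day". Its dose term is set by arm, from 50 to 200 mg. The double-blind lansoprazole formulas are built the same way from capsules. Duration is "Date of last intake of study treatment in DB phase – date of first intake of study treatment in DB phase + 1".

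The protocol describes a different pattern of supply:

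- Table 1 (Protocol 1.3) marks the row "Patients provided with study drugs for blinded phase" at Visits 2, 3 and 4.
- Protocol 4.1 gives each patient 35 days of drug for a 28-day phase, including one extra blister pack at Visit 2.
- Protocol 6.2 says of that pack: "Patients should return this additional blister pack for accountability at every visit and returned on Visit 5".
- Protocol 6.4 has patients bring leftover tablets and capsules to each visit, and bases compliance on what remains.

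One SAP formula is worded differently. Overall lansoprazole compliance (4.9.2) subtracts capsules returned from capsules dispensed without limiting either to the start or end of a phase.

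**The concern.** A start/end rule suits a phase with one dispensing and one return. The open-label phase is like that: lansoprazole is provided only at Visit 5, and the same phrase works there. The double-blind phase has three dispensing visits. A programmer who follows the text leaves the Visit 3 and Visit 4 drug out of the numerator, while the denominator still runs over the whole phase.

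At stake are the tables that show how much drug each arm took in a dose-finding study. Total dose is tabulated on the Safety Analysis Set and compliance on the FAS. The SAP amendment keeps these formulas in force, because it follows the SAP unless it states otherwise, and its section 4.4 extends the compliance summary to FAS erosive and FAS erosive PR.

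**Working it through.** The documents state no compliance figure to reproduce. Their related figures agree with each other: twice 25, 50, 75 and 100 mg gives the SAP's daily doses of 50, 100, 150 and 200 mg, and 35 − 28 = 7 days for the spare pack.

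**Inputs**

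- Tablets per day: 4 (SAP 4.9.1, "in the DB phase, patients are supposed to take 4 tablets of X842 (or dummy) per day"); capsules per day: 1.
- Total supply: 35 days = 140 tablets (Protocol 4.1).
- Spare pack: 7 days × 4 = 28 tablets, or 7 capsules.
- Assumption: the regular Visit 2 supply is *b* days, and Visits 3 and 4 supply the other 28 − *b*. The documents do not give *b*. I use 7 days (packs to cover visit to visit) and 14 days as a range.

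**1. Literal reading, adherent for 28 days, spare pack returned unopened at the end**

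Score = [4(*b* + 7) − 28] / (4 × 28) = *b* / 28.

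- *b* = 7: (56 − 28)/112 = 25%. Capsules: (14 − 7)/28 = 25%.
- *b* = 14: (84 − 28)/112 = 50%.

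The score is below 100% for any split in which Visits 3 and 4 supply part of the 28 days. Across the permitted visit window, with *b* = 7, it runs from (56 − 36)/104 = 19.2% at 26 days to (56 − 8)/132 = 36.4% at 33 days.

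**2. Total X842 dose, same patient, *b* = 7**

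Literal: 28 tablets × daily dose / 4. Actual: 112 tablets × daily dose / 4.

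| Arm (BID) | Literal | Actual |
|---|---|---|
| 25 mg | 350 mg | 1,400 mg |
| 50 mg | 700 mg | 2,800 mg |
| 75 mg | 1,050 mg | 4,200 mg |
| 100 mg | 1,400 mg | 5,600 mg |

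**3. All dispensings minus all returns**

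(140 − 28)/112 = 100%, and the total doses are the actual column above.

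**4. All dispensings minus end-of-phase returns only**

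Suppose a patient misses 8 tablets and hands them in for good at Visit 3. The score is (140 − 28)/112 = 100%, against a true 104/112 = 92.9%. Correcting only the dispensing half would therefore overstate compliance.

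**5. Agreement between the SAP's own formulas**

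Take an adherent lansoprazole patient with *b* = 7, 28 days in each phase and 28 open-label capsules (assumed). Literal double-blind compliance is 25%, open-label is 28/28 = 100%, and Overall is (35 + 28 − 7)/56 = 100%. Total lansoprazole dose, defined as the sum of the two phases, is 210 + 840 = 1,050 mg, against 56 × 30 = 1,680 mg taken.

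**6. Adherent patient who stops after 10 days, *b* = 7**

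- All dispensings minus all returns, Visit 3 drug received: (84 − 44)/40 = 100%.
- Literal, Visit 3 drug received: (56 − 44)/40 = 30%.
- Literal, Visit 3 drug not received: (56 − 16)/40 = 100%.
- Against the planned 28 days: 40/112 = 35.7%.

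**The case against.** The strongest reply is that nobody would program the literal rule. Both terms begin with *Sum of*, the surrounding prose speaks only of units dispensed and returned, and the Overall lansoprazole formula carries no start/end limit. On that view a sum over visits was meant, and the adherent patient scores 100%. This is probably what was intended, and it stands against presenting 25% as the result the SAP will produce. It does not remove the conflict: the same phrase is literally right for the open-label phase, and the return half remains unclear even when the dispensings are summed.

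A reader might infer three stronger points. The documents do not support them.

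- *The formula gives adherent patients 25% while early stoppers get 100%.* These figures generally come from different readings. Where the literal rule gives the adherent patient 25%, the Day-10 stopper who received Visit 3 drug gets 30%.
- *Dividing by days to last intake is an error that hides early stopping.* SAP 4.9.2 says compliance is based on duration of exposure, so it measures adherence while on treatment. Exposure duration is summarized by phase (SAP 4.9.1), withdrawals from study treatment by phase and reason, and the last dose date is listed for discontinuations (SAP 4.4.1). Total dose is not divided by days at all.
- *The spare pack is subtracted at Visits 3, 4 and 5, giving (140 − 84)/112 = 50%.* This needs a pack that is shown and taken home again to be logged as a return each time. Nothing in the documents says that it is.

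**Conclusion.** The double-blind numerators are wrong as written. Followed literally, they understate compliance and total dose for an adherent patient under any split that leaves part of the regular supply to Visits 3 and 4. The size depends on the regular Visit 2 supply, which the documents do not state: 25% to 50% of the true value at 28 days for 7 to 14 days' supply, with the spare pack returned unopened. If the program sums all dispensings and all final returns, there is no distortion.

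The consequence is limited to descriptive exposure and compliance tables and listings. The primary dose-response model in SAP 4.10.2 has treatment, LA grade and center as factors and no compliance term. A compliance-based deviation rule could carry the problem into the PPS, but any such rule would sit in the separate Protocol Deviation Specification, which is not among the documents. The denominator is a stated choice that needs a label, not a correction.

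**What to change.** In SAP 4.9.1 and 4.9.2, change the numerator of the four double-blind formulas (total dose and compliance, for tablets and for capsules) to all units dispensed at Visits 2 to 4 minus all units finally returned during the double-blind phase. State that each unit is counted once and that the spare pack counts as returned only at Visit 5. Apply the same counting rule to the Overall lansoprazole compliance formula, which is otherwise sound; Overall total dose then follows from its parts.

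Label the percentage as compliance while on treatment. A second percentage against planned duration is optional.

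The cost is a few formula lines and the matching derivation code, with no new data. If the tables already exist, check which rule the program used and rerun them only if it was not the sum over visits.

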4.10 Efficacy Evaluation

4.10.1 Analysis and Data Conventions

The primary study objective is to estimate the X842 dose for Phase 3 study with good precision, and hence comparison of different doses of X842 to the active comparator arm (lansoprazole 30 mg) will not

involve any formal statistical testing. Nevertheless, all results for comparator arm will be included in efficacy evaluation summaries.

4.10.1.1 Multi-center Studies

This study is conducted in many sites, and the randomization was not initially stratified by site. After 128 patients were randomised, a new randomisation scheme with stratification by site was put in place to ease the treatment supply on site. Randomisation was balanced by site to allow the clinical supplies team to better predict the required material types and make them available at each site before a patient is randomised.

For the primary efficacy variable, the statistical models to be used for the estimation of dose-response relationship will adjust for differences between centers, by including 'Center' as a main effects term in the model. Adjustment for center will also be performed, wherever possible, in the analysis of the secondary efficacy variables.

Pooling will be applied to deal with small centers. Countries with less than 20 patients will be grouped. The term 'Center' will be used to define the resulting pseudo-centers, for the summaries and analyses.

Descriptive summaries of primary efficacy variable data by treatment group and center will be provided.

4.10.1.2 Adjustments for Covariates

The primary efficacy analysis will be adjusted for the following baseline covariates:

1. Center
2. Erosive esophagitis due to GERD LA grade C or D, erosive esophagitis due to GERD LA grade A or B who are partial responders to PPI treatment

4.10.1.3 Handling of Dropouts or Missing Data

Primary endpoint:

The number and percentage of patients with missing data for the primary endpoint will be summarized by treatment group, by LA grade, overall and by major reason.

A patient data listing will be provided showing all patients with missing values for the primary endpoint. For these patients, the listing will provide important baseline characteristics, the recorded reason(s) for study discontinuation and the timing of study discontinuation.

In a primary analysis, missing healing results will be replaced with a non-responder approach. If there are more than 5% of patients with missing healing results, a sensitivity analysis will also be performed (tipping point method). Scenarios assuming probability of response 20%, 40%, 60%, 80% and 100% will be simulated. Fifty datasets for each probability will be generated, and for each one, an analysis will be conducted, Rubin rules will be used to combine the results.

Secondary endpoint: QOLRAD

Handling of missing values is described in section 4.10.3.1.

Secondary endpoint: mRESQ-eD

Handling of missing values is described in section 4.10.3.2.

4.10.1.4 Multiple Comparisons/Multiplicity

No formal statistical testing is planned. Hence no adjustments for multiplicity are required.

4.10.1.5 Interim Analyses

No interim analysis.

4.10.1.6 Examination of Subgroups

The uniformity of the treatment effect for the primary efficacy variable will be examined for the following subgroups:

1. Age (<60 years, \geq 60 years)
2. Sex (Male, Female)
3. Erosive esophagitis due to GERD LA grade C or D, erosive esophagitis due to GERD LA grade A or B who are partial responders to PPI treatment.

Summaries of the primary efficacy variable by treatment group and subgroup will be produced.

Summaries of the secondary endpoints Percentage of heartburn-free 24-hour days during the Weeks 1-8 based on eDiary (mRESQ-eD) and Percentage of 24-hour days with at most mild heartburn symptoms during the Weeks 1-8 based on eDiary (mRESQ-eD) by treatment group and subgroup will also be produced.

Statistical modeling of dose-response will be performed on subgroups defined by LA grade. No formal statistical analysis will be performed within the other subgroups.

